2 ELIGIBILITY ASSESSMENT AND ENROLLMENT

2.1 ELIGIBILITY CRITERIA

- 2.1.1 Inclusion Criteria
- 2.1.1.1 Patients must have a confirmed diagnosis of chronic lymphocytic leukemia/small lymphocytic lymphoma that expresses CD20 as confirmed by new/fresh peripheral blood sample collection and review by Laboratory of Pathology, NCI
- 2.1.1.2 Measurable or evaluable disease (see Section 6.3)
- 2.1.1.3 Patients must have received prior treatment required as follows: CLL that is refractory or relapsed following therapy with a BTK inhibitor OR have relapsed/refractory CLL and are intolerant of BTK inhibitor therapy; in addition, patients with del(17p) must also be refractory or relapsed after, or intolerant to, therapy with venetoclax; patients who have received prior obinutuzumab are eligible regardless of response to the drug.
- 2.1.1.4 Active disease requiring treatment, as defined by at least one of the following (per IWCLL 2018 consensus criteria):
 - Evidence of progressive marrow failure as manifested by the development of, or worsening of, anemia (Hb <10 g/dL) and/or thrombocytopenia (platelet counts $<100 \times 10^9$ /L).
 - Massive (i.e., ≥6 cm below the left costal margin) or progressive or symptomatic splenomegaly.
 - Massive nodes (i.e., ≥10 cm in longest diameter) or progressive or symptomatic lymphadenopathy.
 - Progressive lymphocytosis with an increase of ≥50% over a 2-month period, or lymphocyte doubling time (LDT) <6 months.
 - Autoimmune complications including anemia or thrombocytopenia poorly responsive to corticosteroids.
 - Symptomatic or functional extranodal involvement (eg, skin, kidney, lung, spine).
 - Disease-related symptoms as defined by any of the following:
 - Unintentional weight loss $\ge 10\%$ within the previous 6 months.
 - Significant fatigue (ie, ECOG performance scale 2 or worse; cannot work or unable to perform usual activities).
 - o Fevers 38.0°C for 2 or more weeks without evidence of infection.
 - Night sweats for ≥ 1 month without evidence of infection.
- 2.1.1.5 ≥18 years of age on day of signing informed consent

NOTE: Because no dosing or adverse event data are currently available on the use of rhIL-15 in combination with obinutuzumab in patients <18 years of age, children are excluded from this study, but will be eligible for future pediatric trials

Version Date: 09/14/2021

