6.3 RESPONSE CRITERIA

Responses for spleen and lymphadenopathy will be assessed using CT scan measurements and not physical exam. Response assessments will be made by IWCLL 2018 guidelines(9). Response includes complete response (CR), and partial response (PR).

	Criteria of response								
Response	CR	PR	PD	SD					
Group A ^A									
Lymphadenopathy ^B	None >1.5cm	Decrease ≥50%	Increase ≥50% or any new lesion > 1.5cm	Change of - 49% to +49%					
Liver and/or spleen size	Spleen size <13cm; liver size normal	Decrease ≥50% (from baseline)	Increase ≥50% from baseline or from response	Change of - 49% to +49%					
Constitutional symptoms	None	Any	Any	Any					
Circulating lymphocyte count	Normal	Decrease ≥50% from baseline	Increase ≥50% over baseline ^D	Change of - 49% to +49%					
Group B ^A									
Platelet count	>100,000/ μL	>100,000/ µL or increase ≥50% over baseline	Decrease ≥50% from baseline secondary to CLL	Change of - 49% to +49%					

Version Date: 09/14/2021

Criteria of response									
Response	CR	PR	PD	SD					
Hemoglobin	>11.0 g/dL (untransfused and without erythropoietin)	>11.0 g/dL or increase ≥50% over baseline	Decrease ≥50% from baseline secondary to CLL	Increased but <11.0 g/dL or <50% over baseline, or decrease <2 g/dL					
Bone marrow ^C	Normocellular, no CLL cells, no B-lymphoid nodules.	Presence of CLL cells, or of B-lymphoid nodules, or not done	Increase of CLL cells by ≥50% on successive biopsies	No change in marrow infiltrate					

Footnotes:

CR (**complete response**): Disease-related constitutional symptoms resolved and all above criteria met, includes bone marrow biopsy

CRi (complete response with incomplete marrow recovery): CR with incomplete hematopoietic recovery **PR (partial response):** Two criteria from Group A if abnormal at baseline plus one of the criteria from Group B must be met, requires the absence of growth factor or transfusion support

SD (stable disease): Defined as not achieving CR, or PR, but not fulfilling the criteria for PD will be considered to have stable disease (which is equivalent to no response)

PD (**progressive disease**): One criteria from Group A or B are met or development of transformation to a more aggressive histology

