6.3.1 Best Overall Response

The best overall response is the best response recorded from the start of the treatment until disease progression/recurrence (taking as reference for progressive disease the smallest measurements recorded since the treatment started). The patient's best response assignment will depend on the achievement of both measurement and confirmation criteria.

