6.3.3 Progression-Free Survival

Progression-free survival (PFS) is defined as the duration of time from the date of study enrollment until time of disease relapse, disease progression, or death, whichever occurs first.

A Group A criteria define the tumor load. Group B criteria define the function of the hematopoietic system or marrow. For CR, all of the criteria have to be met.

^B Sum of the product (SPDs) of up to 6 lymph nodes as evaluated by CT scans. If CT is unavailable, the absence of enlarged lymph nodes (> 1.5cm) documented by physical exam is acceptable. For progression, SPDs should increase by >50% and at least one of the target lesions should be pathologically enlarged (> 1.5cm).

^C Complete response requires confirmation with bone marrow biopsy.

^D For progression, absolute lymphocyte count should increase ≥ 50% from nadir confirmed with two consecutive assessments within 3 months. CD19 B cell count should be >5,000/μL in at least one of the two assessments. Abbreviations and definitions:

Version Date: 09/14/2021

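### The progression reference in Sections 6.3.1 and 6.3.2 runs the wrong way for platelets and hemoglobin and conflicts with the Section 6.3 table, whose hemoglobin SD and PD cells also leave a gap

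*Combined protocol and SAP*

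**What the plan says.** In the Section 6.3 table the PD cell is the same for platelets and hemoglobin: "Decrease ≥50% from baseline secondary to CLL". One criterion from either group is enough for PD. For hemoglobin the PR cell reads ">11.0 g/dL or increase ≥50% over baseline" and the SD cell reads "Increased but <11.0 g/dL or <50% over baseline, or decrease <2 g/dL". The overall SD definition is residual: "Defined as not achieving CR, or PR, but not fulfilling the criteria for PD will be considered to have stable disease".

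Other rows of the table follow loss of response. Liver/spleen PD is "Increase ≥50% from baseline or from response". Footnote D to the table says that for progression the "absolute lymphocyte count should increase ≥ 50% from nadir confirmed with two consecutive assessments within 3 months".

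Section 6.3.1 (best overall response) and Section 6.3.2 (duration of response) each add a general reference: "taking as reference for progressive disease the smallest measurements recorded since the treatment started". Sections 6.3.3 (PFS) and 6.3.4 (EFS) name no reference.

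Cytopenia is one of the routes into the trial. Section 2.1.1.4 lists "Evidence of progressive marrow failure as manifested by the development of, or worsening of, anemia (Hb <10 g/dL" and, in the same item, platelets below 100 × 10⁹/L. The entry floors in Section 2.1.1 are 50,000/mcL for platelets and 9 g/dL for hemoglobin.

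**The concern.** A smallest-value reference protects against missing regrowth when disease is measured by size or by lymphocyte count. Applied to platelets or hemoglobin it does the opposite: it takes the deepest trough as the starting point, so a later fall caused by CLL looks small or even looks like a rise. Since DOR is defined with that reference and the table uses baseline, two readers could date the end of the same response differently.

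The hemoglobin row has its own problem. Its SD and PD cells use different scales (g/dL and percent) and do not meet.

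Finally, in a patient treated because of marrow failure, baseline is already the diseased value, so losing the whole hematologic gain does not by itself count as progression. DOR, PFS and EFS are secondary endpoints built on this definition. Any resulting error lengthens them.

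**Working it through.** The plan gives no figure here to reproduce. The check applies the rules to example patients. The paths are assumed; the entry values respect the protocol's limits.

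**Rule.** PD on a count if (reference − current) / reference ≥ 0.50.
- Table (6.3): reference = baseline.
- 6.3.1 and 6.3.2 read literally: reference = lowest value since treatment start.

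**1. Conflict between the two references.** Platelets 80,000 (entry) → 30,000 (drug nadir) → 150,000 (response) → 40,000 (CLL relapse).
- From baseline: 40/80 − 1 = −50%, so PD.
- From smallest: 40/30 − 1 = +33%, so not PD.
- The nadir itself is 30/80 − 1 = −62.5%. It is kept out of PD only because it is attributed to drug and not to CLL.
- For this patient the rules disagree for any relapse count above 0.5 × 30,000 = 15,000 and up to 0.5 × 80,000 = 40,000.

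**2. Gap in the hemoglobin row.** SD allows a fall under 2 g/dL; PD needs a fall of at least 0.5 × baseline.
- Entry 9.0: SD covers values above 7.0; PD starts at 4.5. Values from 7.0 down to just above 4.5 (falls of 22% up to just under 50%) fit neither cell.
- Entry 12.0: SD covers falls to above 10.0; PD starts at 6.0. Values from 10.0 down to just above 6.0 fit neither.
- These patients become SD only through the residual definition.

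**3. Recovery, then return to the entry count.**
- Platelets 60,000 → 150,000 → 60,000: 0% from baseline, not PD. From the smallest value it is 0% if the on-treatment low was 60,000 and +100% if it was 30,000, so not PD either way.
- For PD from baseline this patient must reach 30,000, which is 1 − 30/150 = 80% below the peak. With a low of 30,000, the smallest-value rule would require 15,000.
- Hemoglobin 9.0 → 12.5 → 9.0: 0% from baseline, not PD.

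**4. Would a reference to the best value in response solve it?** Only in part.
- Platelets 60,000 → 150,000 → 60,000: −60% from peak, now PD.
- Platelets 80,000 → 150,000 → 80,000: −47%, still not PD.
- Hemoglobin 12.5 → 9.0: −28%, still not PD. A return to 9.0 would need a peak of 18 g/dL.
- Platelets 300,000 → 150,000: −50%, which meets the number although the count is still above the 100,000/µL response level.

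**The case against.** The strongest reply is that a specific table cell governs over a general parenthesis. On that reading the smallest-value phrase concerns lesion size, counts stay on baseline, and the conflict in step 1 disappears. The phrase is also absent from the PFS and EFS definitions. This is a sensible reading, but the text does not state it, and DOR carries the phrase explicitly. The reply supports writing that reading down.

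A reader might infer that a cytopenic patient who recovers and relapses is never scored as progressed on counts. The documents do not support that: a fall to half of baseline still scores, as the 80,000 → 40,000 example shows. The same relapse can also be PD through nodes, any new lesion over 1.5 cm, spleen measured from response, lymphocytes from nadir, marrow or transformation. PFS and EFS count relapse, and DOR recurrence, alongside progression, although these terms are not defined. So the effect is a possible delay. The delay is realistic because Section 3.9 schedules CT after cycle 6 and leaves later imaging to discretion at 6 months and then yearly, while blood counts are taken at follow-up visits every 3 months in the first year.

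It is also tempting to conclude that the table must adopt a best-value reference. Step 4 shows that this leaves hemoglobin unrepaired and, without a floor, can label a fall above the response level as meeting the PD number. Whether a baseline reference departs from the guideline that the protocol follows cannot be judged from these documents.

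Lastly, these are descriptive secondary endpoints in a single-arm trial of at most 24 patients. That stands, and it limits the weight of the point.

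**Conclusion.** The concern holds as an internal inconsistency with three parts. The smallest-value reference is in the wrong direction for platelets and hemoglobin and, read literally, contradicts the table for DOR. The hemoglobin SD and PD cells do not meet. A return to the entry count after recovery is not PD on counts, which may delay the PD date for DOR, PFS and EFS.

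The size of the effect on those endpoints cannot be computed: the share of patients entering with cytopenia is not given, and the paths above are illustrations. The direction, where there is an effect, is towards longer durations. With at most 24 patients, and DOR estimated in responders only, a few misdated events could shift a Kaplan-Meier curve. The DLT and MTD definitions do not use these criteria and are unaffected.

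**What to change.** 1. In Sections 6.3.1 and 6.3.2, limit the smallest-value reference to nodal, liver/spleen and lymphocyte measurements, and state that platelets and hemoglobin use the reference given in the Section 6.3 table.
2. Reconcile the hemoglobin SD and PD cells with each other and with the response guideline. The citation needs the same check: Section 6.3 names the 2018 guideline but cites reference 9, which Section 15 lists as the 2008 publication; the 2018 one is reference 10.
3. Optional: add a from-response reference for platelets, like the one in the liver/spleen row. If adopted, it should also require the count to be below the response level of 100,000/µL, so that a fall within the normal range is not PD.

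The cost is wording in one table and two sentences, using blood counts already collected. Some PD dates may move slightly earlier. Because Section 3.10.1 lists confirmed hematologic progression as a reason for removal from therapy, the sponsor should check that section against the reconciled wording.

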6.3.1 Best Overall Response

The best overall response is the best response recorded from the start of the treatment until disease progression/recurrence (taking as reference for progressive disease the smallest measurements recorded since the treatment started). The patient's best response assignment will depend on the achievement of both measurement and confirmation criteria.

6.3.2 Duration of Response

The duration of response (DOR) is measured from the time measurement criteria are met for CR, CRi, or PR (whichever is recorded first) until the first date that recurrent or progressive disease is objectively documented (taking as reference for progressive disease the smallest measurements recorded since the treatment started), death, or, in the absence of PD, date of last assessment.

6.3.3 Progression-Free Survival

Progression-free survival (PFS) is defined as the duration of time from the date of study enrollment until time of disease relapse, disease progression, or death, whichever occurs first.

A Group A criteria define the tumor load. Group B criteria define the function of the hematopoietic system or marrow. For CR, all of the criteria have to be met.

^B Sum of the product (SPDs) of up to 6 lymph nodes as evaluated by CT scans. If CT is unavailable, the absence of enlarged lymph nodes (> 1.5cm) documented by physical exam is acceptable. For progression, SPDs should increase by >50% and at least one of the target lesions should be pathologically enlarged (> 1.5cm).

^C Complete response requires confirmation with bone marrow biopsy.

^D For progression, absolute lymphocyte count should increase ≥ 50% from nadir confirmed with two consecutive assessments within 3 months. CD19 B cell count should be >5,000/μL in at least one of the two assessments. Abbreviations and definitions:

Version Date: 09/14/2021

6.3.4 Event-Free Survival

Event-free survival (EFS) is defined as the duration of time from the date of study enrollment until time of disease relapse, disease progression, alternative therapy for lymphoma given (such as radiation), or death, whichever occurs first.

6.4 TOXICITY CRITERIA

The following adverse event management guidelines are intended to ensure the safety of each patient while on the study. For **non-hematologic toxicities**, the descriptions and grading scales found in the revised NCI Common Terminology Criteria for Adverse Events (CTCAE) version 5.0 will be utilized for AE reporting. All appropriate treatment areas should have access to a copy of the CTCAE version 5.0. A copy of the CTCAE version 5.0 can be downloaded from the CTEP web site (http://ctep.cancer.gov/protocolDevelopment/electronic applications/ctc.htm).

For **hematologic** toxicities, the updated IWCLL guidelines will be used(10):

Grade ¹	Decrease in platelets ² or Hb ³ (nadir) from baseline value (%)	Absolute neutrophil count/ μL ⁴ (nadir)
0	No change – 10%	≥2,000
1	11%-24%	≥1,500 and <2,000
2	25%-49%	≥1,000 and <1,500
3	50%-74%	≥500 and <1,000
4	≥75%	<500

Footnotes:

7 NIH REPORTING REQUIREMENTS/DATA AND SAFETY MONITORING PLAN

7.1 **DEFINITIONS**

Please refer to definitions provided in Policy 801: Reporting Research Events found here.

7.2 OHSRP OFFICE OF COMPLIANCE AND TRAINING/ IRB REPORTING

7.2.1 Expedited Reporting

Please refer to the reporting requirements in Policy 801: Reporting Research Events and Policy 802 Non-Compliance Human Subjects Research found here. Note: Only IND Safety Reports that meet the definition of an unanticipated problem will need to be reported per these policies.

¹ Grades: 1, mild; 2, moderate; 3, severe; 4, life-threatening; 5, fatal. Death occurring as a result of toxicity at any level of decrease from baseline will be recorded as grade 5.

² Platelet counts must be below normal levels for grades 1-4. If, at any level of decrease the platelet count is $<20.000/\mu$ L, this will be considered grade 4 toxicity, unless a severe or life-threatening decrease in the initial platelet count (e.g., $20.000/\mu$ L) was present at baseline, in which case the patient is not evaluable for toxicity referable to platelet counts.

³ Hb levels must be below normal levels for grades 1-4. Baseline and subsequent Hb determinations must be performed before any given transfusions. The use of erythropoietin is irrelevant for the grading of toxicity, but should be documented.

⁴ If the absolute neutrophil count (ANC) reaches < $1.000/\mu L$, it should be judged to be grade 3 toxicity. Other decreases in the white blood cell count, or in circulating granulocytes, are not to be considered, since a decrease in the white blood cell count is a desired therapeutic end point. A gradual decrease in granulocytes is not a reliable index in CLL for stepwise grading of toxicity. If the ANC was < $1.000/\mu L$ prior to therapy, the patient is not evaluable for toxicity referable to the ANC. The use of G-CSF is irrelevant for the grading of toxicity, but should be documented.

Version Date: 09/14/2021

7.2.2 IRB Requirements for PI Reporting at Continuing Review

Please refer to definitions provided in Policy 801: Reporting Research Events found here.

7.3 NCI CLINICAL DIRECTOR REPORTING

Problems expeditiously reported to the OHSRP in iRIS will also be reported to the NCI Clinical Director. A separate submission is not necessary as reports in iRIS will be available to the Clinical Director.

In addition to those reports, all deaths that occur within 30 days after receiving a research intervention should be reported via email to the Clinical Director unless they are due to progressive disease.

To report these deaths, please send an email describing the circumstances of the death to [name] at [contact] within one business day of learning of the death.

7.4 NIH REQUIRED DATA AND SAFETY MONITORING PLAN

7.4.1 Principal Investigator/Research Team

The clinical research team will meet at least weekly when patients are being actively treated on the trial to discuss each patient. Decisions about dose level enrollment and dose escalation if applicable will be made based on the toxicity data from prior patients.

All data will be collected in a timely manner and reviewed by the principal investigator or a lead associate investigator. Events meeting requirements for expedited reporting as described in section 7.2.1 will be submitted within the appropriate timelines.

The principal investigator will review adverse event and response data on each patient to ensure safety and data accuracy. The principal investigator will personally conduct or supervise the investigation and provide appropriate delegation of responsibilities to other members of the research staff.

8 SPONSOR SAFETY REPORTING

8.1 **DEFINITIONS**

8.1.1 Adverse Event

Any untoward medical occurrence in a patient or clinical investigation subject administered a pharmaceutical product and which does not necessarily have a causal relationship with this treatment. An adverse event (AE) can therefore be any unfavorable and unintended sign (including an abnormal laboratory finding), symptom, or disease temporally associated with the use of a medicinal (investigational) product, whether or not related to the medicinal (investigational) product (ICH E6 (R2)).

8.1.2 Serious Adverse Event

An adverse event or suspected adverse reaction is considered serious if in the view of the investigator or the sponsor, it results in any of the following

- Death
- A life-threatening adverse event (see 8.1.3)
- Inpatient hospitalization or prolongation of existing hospitalization
 - o A hospitalization/admission that is pre-planned (i.e., elective or scheduled surgery arranged prior to the start of the study), a planned hospitalization for pre-existing

Version Date: 09/14/2021

condition, or a procedure required by the protocol, without a serious deterioration in health, is not considered a serious adverse event.

- o A hospitalization/admission that is solely driven by non-medical reasons (e.g., hospitalization for patient convenience) is not considered a serious adverse event.
- Emergency room visits or stays in observation units that do not result in admission to the hospital would not be considered a serious adverse event. The reason for seeking medical care should be evaluated for meeting one of the other serious criteria.
- Persistent or significant incapacity or substantial disruption of the ability to conduct normal life functions
- A congenital anomaly/birth defect
- Important medical events that may not result in death, be life-threatening, or require hospitalization may be considered a serious adverse drug experience when, based upon appropriate medical judgment, they may jeopardize the patient or subject and may require medical or surgical intervention to prevent one of the outcomes listed in this definition.

8.1.3 Life-threatening

An adverse event or suspected adverse reaction is considered "life-threatening" if, in the view of either the investigator or sponsor, its occurrence places the patient or subject at immediate risk of death. It does not include an adverse event or suspected adverse reaction that, had it occurred in a more severe form, might have caused death. (21CFR312.32).

8.1.4 Severity

The severity of each Adverse Event will be assessed utilizing the CTCAE version 5.

8.1.5 Relationship to Study Product

All AEs will have their relationship to study product assessed using the terms: related or not related.

- Related There is a reasonable possibility that the study product caused the adverse event. Reasonable possibility means that there is evidence to suggest a causal relationship between the study product and the adverse event.
- Not Related There is not a reasonable possibility that the administration of the study product caused the event.

